For participants who early terminate from the placebo-controlled phase, an in-person Early Termination Visit and a Follow-up Safety Call should be conducted. At the Early Termination Visit the same procedures as described for the Week 24 visit should be conducted. At the Follow-up Safety Call, information on clinical status should be collected.

For participants who early terminate from the OLE, an in-person Early Termination Visit and a Follow-up Safety Call should be conducted. At the Early Termination Visit the same procedures as described for the Final visit should be conducted. At the Follow-up Safety Call, information on clinical status should be collected.

Total Planned Trial Duration

For participants completing only the placebo-controlled Treatment Period of the study, the planned amount of time for participation in the trial is 34 weeks, or about 8 months. This duration assumes a 6-week screening window, a 24-week placebo-controlled treatment period, and a 28-day safety follow-up period for those participants who do not enter the OLE. Participants will complete approximately 10 study visits during the placebo-controlled period of the study.

SCHEDULE OF ACTIVITIES – 24-WEEK PLACEBO-CONTROLLED PHASE

As per the Schedule of Activities (SOA) below, visits must occur every 4 weeks and will be alternatively clinic-, phone-, or telemedicine-based, as applicable. There is a maximum 24-week duration of placebo-controlled treatment for a Regimen.

| Activity | Master Protocol or Regimen-Specific | Master Protocol Screening ¹ | Regimen Specific Screening ¹ | Baseline | Week 2 ² | Week 4 ^{18,19} | Week 8 ^{18,19} | Week 12 | Week 16 ^{18,19} | Week 20 | Week 24 or Early Term. Visit ^{3, 18} | Follow-up Safety Call ^{3,4} |
|---|-------------------------------------|--|---|----------|---------------------|-------------------------|-------------------------|-----------|--------------------------|------------|---|--------------------------------------|
| | | Clinic | Clinic | Clinic | Phone | Clinic | Clinic | Phone | Clinic | Phone | Clinic | Phone |
| | | -42 to -1 Days | -41 to 0 Days | Day 0 | Day 14 ±3 | Day 28 ±7 | Day 56 ±7 | Day 84 ±3 | Day 112 ±7 | Day 140 ±3 | Day 168 ±7 | 28±7 days after last dose |
| Written Informed Consent – Placebo-controlled Period ⁵ | Master | X | X | | | | | | | | | |
| Written Informed Consent - OLE | Regimen | | | | | | | | X | | | |
| Inclusion/Exclusion Review | Master | X | X ⁶ | | | | | | | | | |

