3.2 End of Participation Definition

A participant is considered to have ended his or her participation in the placebo-controlled period of the Regimen if they:

- Complete planned placebo-controlled period visits, as described in the SOA, including participants on or off study drug
- Early terminate from the study and complete the Early Termination Visit and Follow-Up Phone call as described in Section 6.1.11
- Withdraw consent to continue participation in the study, or are lost to follow-up

If a participant initiates open-label study drug in the OLE period, he or she is considered to have completed his or her participation in the OLE period of the Regimen if they choose to discontinue participation or if all planned OLE period visits, including the last visit or the last scheduled procedure shown in the SOA, have been completed.

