6.1.10 Follow-Up Safety Call

Participants will have a Follow-Up Safety Call 28±7 days after their last dose of study drug. Only those participants NOT continuing on in the Open Label Extension will have the Follow-Up Safety Call following the end of their participation in the placebo-controlled portion of the trial. The following procedures will be performed:

- Assess and document AEs, including Key Study Events (*see section 10.3 of Master Protocol*)

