6.1.11 Process for Early Terminations

Participants who early terminate from the study and do not complete the protocol per ITT will be asked to be seen for an in-person Early Termination Visit and complete a Follow-Up Safety Call. If a participant is not able to be seen in-person, safety assessments and others that can be conducted remotely should be performed.

The in-person Early Termination Visit should be scheduled as soon as possible after a participant early terminates. If the participant early terminates during the placebo-controlled portion of the Regimen, all assessments that are collected at the Week 24 in-clinic visit should be conducted. The Follow-Up Safety Call should be completed approximately 28±7 days after the last dose of study drug. If the participant terminates early during the OLE period, all assessments that are intended for collection at the OLE Week 24 in-clinic visit should be conducted. The Follow-Up Safety Call should be completed approximately 28±7 days after the last dose of IP.

If the Early Termination Visit occurs approximately 28±7 days after the last dose of study drug, the information from the Follow-Up Safety Call can be collected during the Early Termination Visit, and a separate Follow-Up Safety Call does not need to be completed. If the in-person Early Termination Visit does not occur within 28±7 days of the last dose of study drug, the Follow-Up Safety Call should occur approximately 28±7 days after the last dose of study drug and the Early Termination Visit will be completed after the Follow-Up Safety Call.

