6.1.12 Criteria for Participant Termination

Participants MUST discontinue the IP (and non-investigational product at the discretion of the SI) for any of the following reasons:

- Withdrawal of informed consent (participant's decision to withdraw for any reason)
- Any clinical adverse event (AE), laboratory abnormality or intercurrent illness which, in the opinion of the SI or sponsor, indicates that continued participation in the study is not in the best interest of the participant

- Disease progression, which, in the opinion of the SI or sponsor, indicates that continued participation in the study is not in the best interest of the participant
- Pregnancy
- Termination of the study by the Sponsor
- Loss of ability to freely provide consent through imprisonment or involuntary incarceration for treatment of either a psychiatric or physical (e.g., infectious disease) illness

All participants who discontinue study treatment earlier than Week 24 should comply with protocol specified Early Termination procedures as appropriate, outlined in the Schedule of Activities.

An exception to the requirement for End of Treatment procedures is when a participant withdraws consent for all study procedures or loses the ability to consent freely (i.e., is imprisoned or involuntarily incarcerated for the treatment of either a psychiatric or physical illness).

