9 SAFETY AND ADVERSE EVENTS

9.1 Adverse Events of Special Interest – Thyroid Function

Reversible changes in thyroid function tests were observed during the preclinical studies and clinical studies with verdiperstat. Based on prior trials, a small percentage of participants may be expected to develop mild (subclinical) hypothyroidism generally with serum TSH < 10 mIU/L. Laboratory monitoring of thyroid function will be performed and documented throughout this study. Site Investigators should review TSH levels and note the trend over time. The Central Laboratory will flag any TSH \geq ULN, and T3 and free T4 analysis should be performed.

Any significant abnormal findings should be discussed with the study Medical Monitor and may be followed up as per local practice (e.g., investigations and consultation with endocrinologist). In cases of suspected hypothyroidism, repeat thyroid function tests should be measured and levothyroxine replacement therapy should be considered. Initiation of treatment is at the discretion of the SI.

Potential initiation of levothyroxine (T4) replacement therapy may be considered according to the following guidelines:

- For a serum TSH between 5 and 10, levothyroxine 0.05 mg daily (50 mcg) is a reasonable dose to prescribe.
- For a serum TSH between 10 and 20, levothyroxine 0.075 mg daily (75 mcg) is a reasonable dose to prescribe.
- For a serum TSH greater than 20, many physicians would feel more comfortable having an endocrinologist treat such participants.

If signs/symptoms of hypothyroidism (i.e. adverse event, initiation of levothyroxine) and/or significant changes in thyroid function develop, collection of follow up clinical chemistry samples and/or unscheduled study visits may be warranted. It is recommended to wait for 5 or 6 half-lives (5 – 6 weeks) to retest thyroid function. Serum T3, free T4 and TSH should be monitored in such participants, and the serum TSH assesses whether therapy is adequate.

If there are clinically significant issues with tolerability that are not able to be treated adequately with levothyroxine replacement therapy, the SI may consider modifications to the dosage regimen. Consultation with the Medical Monitor is required. Modifications may include reducing the dose of verdiperstat /matching placebo to 300 mg BID or taking a dose holiday. Any such modifications to the dosage regimen should be noted in the CRF.

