# 6.6 Safety Analyses

#### **6.6.1** Treatment-emergent Adverse Events

Summaries and analyses of treatment-emergent adverse events (TEAE) are the same as specified in the M-SAP with the following revisions.

TEAEs are defined as those adverse events with onset dates in the interval from double-blind treatment initiation to the earliest of the Final Safety Visit, the date the participant dies, early terminates, or is lost to follow-up, 28 days after last dose of study drug, or the date of first dose of study drug during participation in the OLE, if so exposed. Adverse events with onset on the day of double-blind treatment initiation and adverse events with incompletely specified onset date where the ambiguous date spans the day of double-blind treatment initiation or the earliest of the events above that define the end of the treatment-emergence interval will be assumed to be treatment emergent except for those known to precede first exposure to study drug.

In addition to summaries specified in the M-SAP, the following categories of adverse events will be summarized by Medical Dictionary for Regulatory Activities (MedDRA) system organ class and preferred term: (a) all adverse events, including those not classified as TEAEs, (b) fatal TEAEs, and (c) TEAEs that occurred during a participant's COVID-19 infection (defined as 5 days prior to symptom onset to end of COVID-19 symptoms or end of double-blind follow-up, if ongoing).

TEAEs indicating COVID-19 infection are the following: Asymptomatic COVID-19, COVID-19, COVID-19 pneumonia, COVID-19 treatment, Post-acute COVID-19 syndrome, SARS-CoV-

2 antibody test positive, SARS-CoV-2 RNA increased, SARS-CoV-2 sepsis, SARS-CoV-2 test false negative, SARS-CoV-2 test positive, SARS-CoV-2 viraemia, Suspected COVID-19.

Treatment-dependent differences in the proportion of participants experiencing a given type of TEAE will not be tested. Treatment-dependent differences in TEAE incidence rates in units of number per 100 participant years will be estimated as differences rather than ratios, will include comparison-wise 95% confidence intervals with variance estimates obtained by the delta method, and will be provided for overall classes of TEAEs not further classified by MedDRA term (all TEAEs, serious TEAEs, severe TEAEs, TEAEs leading to discontinuation of study drug, TEAEs resulting in death, and TEAEs of special interest) and TEAEs with at least 5% prevalence in the active arm.

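### Does closing the TEAE window at early termination (SAP 6.6.1) leave out adverse events that the trial collects?

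*SAP*

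**What the plan says.** SAP 6.6.1 opens the treatment-emergent window at the first double-blind dose and closes it at "the earliest of the Final Safety Visit, the date the participant dies, early terminates, or is lost to follow-up", or at 28 days past the final dose, or at the first open-label dose, whichever comes first. An AE whose onset date is incomplete and could straddle the closing date is counted as treatment-emergent. The same section also summarises and lists all AEs, whether treatment-emergent or not.

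The protocol requires contacts after early termination. Its summary states: "For participants who early terminate from the placebo-controlled phase, an in-person Early Termination Visit and a Follow-up Safety Call should be conducted". Section 6.1.11 gives the order. First: "The in-person Early Termination Visit should be scheduled as soon as possible after a participant early terminates". Then: "The Follow-Up Safety Call should be completed approximately 28±7 days after the last dose of study drug". At that call, section 6.1.10 has the site "Assess and document AEs, including Key Study Events".

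Protocol 3.2 describes when participation in the placebo-controlled period ends. One of the routes is: "Early terminate from the study and complete the Early Termination Visit and Follow-Up Phone call as described in Section 6.1.11". SAP 6.7.1 uses early termination as one of the ways a participant's study participation ends prematurely, and attaches no date rule to it.

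SAP Section 1 says that the regimen SAP sets out modifications to the Master SAP defaults. Section 6.6.1 is written in that form: as in the Master SAP, with stated revisions.

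**The concern.** The closing rule takes the earliest of several dates, and one of them has no definition in the regimen SAP. Protocol 6.1.11 schedules the Early Termination Visit after the participant early terminates, so the termination date can be read as the day of the decision, with the visit and the safety call still to come. Under an earliest-of rule, that day would close the window. An AE with a known onset after that day, but within 28 days of the last dose, would be collected by the site and then left out of every treatment-emergent class: serious, severe, fatal and special-interest events, and the incidence-rate differences.

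The rule also seems out of step with its neighbours. SAP 6.6.2 tabulates hypothyroid signs or symptoms at visits up to 28 days past the final dose, with no cut at termination, and protocol 9.1 makes thyroid function the AE of special interest. The third exposure definition in SAP 6.7.2 runs to final contact or 28 days, whichever is earlier. Two programmers could therefore close the window on different days for the same participant. SAP 6.7.1 also lists consent withdrawal separately from early termination, while 6.6.1 names only the latter.

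**Working it through.** The plan states no figure to reproduce. The check is how far the two readings of the termination date can differ.

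**Inputs.** Count days from the last dose (day 0).
- *e*: day of early termination. The documents do not give it, so a range is assumed.
- *c*: day of the safety call. Protocol 6.1.11 allows 28±7, so 21 to 35. The schedule in SAP 2.9 shows ±3 for this call, but SAP Section 1 gives the protocol precedence on matters outside analysis, so ±7 is used.
- Fixed limit: day 28 (SAP 6.6.1).
- Assumption: the Final Safety Visit in SAP 6.6.1 is this safety call for a participant who does not enter the open-label phase.

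**Reading A: termination is the decision that precedes the visit and call.**

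Window end = min(*e*, *c*, 28). Without the termination limb it would be min(*c*, 28). Days lost = max(0, min(*c*, 28) − min(*e*, *c*, 28)).

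For example, *e* = 7 and *c* = 28 gives 28 − 7 = 21 days; *e* = 0 and *c* = 21 gives 21 − 0 = 21 days.

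| *e* | Days lost, call on day 21 | Days lost, call on day 28 or 35 |
|---|---|---|
| 0 | 21 | 28 |
| 3 | 18 | 25 |
| 7 | 14 | 21 |
| 14 | 7 | 14 |
| 21 | 0 | 7 |
| 28 | 0 | 0 |

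If the date meant is the Early Termination Visit itself, the same table applies with *e* as the visit day.

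**Reading B: termination is the end of participation under protocol 3.2.** The visit and the call are then complete, so *e* is at or after *c* and min(*e*, *c*, 28) = min(*c*, 28). Days lost = 0.

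**Who could be affected under Reading A.** Only a participant who leaves the study less than 28 days after the last dose, before the safety call, and who then has a contact at which AEs are recorded. Someone who stops drug but stays on study does not reach this limb; the 28-day limit closes that window. An AE with an incomplete onset date that could straddle the closing day is still counted. This leaves AEs with a known later onset, and those remain in the all-AE summary and listing.

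**Which reading fits the documents.** The neighbouring limbs (final safety contact, death, loss to follow-up, start of open-label drug) each mark the end of placebo-controlled observation. Taking early termination the same way matches protocol 3.2 and the disposition wording in SAP 6.7.1. The limb then largely repeats the final safety contact, which does no harm in an earliest-of list.

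**The case for a change.** The strongest argument for a change is that the safety tables should not depend on an inference. Protocol 6.1.11 does put termination first, the regimen SAP outranks the Master SAP where they differ, and protocol 6.1.12 sends anyone who stops treatment before Week 24 through early-termination procedures as appropriate, which blurs the date further. One clarifying phrase would cost almost nothing. What stands is that neither the regimen SAP nor the protocol appendix fixes the date, and that Reading A is possible.

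The supporting points are weaker.

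- **Thyroid tables (SAP 6.6.2).** These record status at visits, while 6.6.1 classifies by onset date. The two can differ for other reasons and need not agree.
- **Exposure (SAP 6.7.2).** Three exposure definitions are given, and none is named as the basis for classifying TEAEs or as the rate denominator. Differing from one of them is not a contradiction.
- **Consent withdrawal.** Protocol 6.1.12 states: "An exception to the requirement for End of Treatment procedures is when a participant withdraws consent for all study procedures". The 28-day limit still bounds the window for such a participant, so it is not left open.
- **A broader rewrite.** Ending the window at the last contact where AEs were assessed would bring its own risk: a fatal event starting after that contact, and learned through vital-status follow-up, could fall outside it.

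An undefined term in a document that lists only modifications does not show that the whole plan leaves it undefined. The Master SAP may supply the date.

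**Conclusion.** No change to the plan follows. The wording leaves one date to be read. The end-of-participation reading, supported by protocol 3.2 and SAP 6.7.1, loses 0 days. The literal alternative loses 0 to 28 days of window per early terminator, and at most 21 if the safety call, taken as the Final Safety Visit, falls on day 21. No collected AE disappears from reporting on either reading, and SAP 6.6.1 does not test differences in TEAE proportions between arms.

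The documents give no early-termination rate, termination timing or event rate, so neither a number of misclassified events nor a bias between arms can be derived. The conclusion rests on two assumptions: that analysts take early termination as the end of placebo-controlled observation, as the neighbouring limbs suggest, and that the Master SAP, not seen here, does not direct otherwise. This is a small gap in wording that competent analysts would fill sensibly.

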| SAE | Serious Adverse Event |

| | |
|-------|---------------------------------|
| SI | Site Investigator |
| SOA | Schedule of Activities |
| SOD | Superoxide dismutase |
| SVC | Slow Vital Capacity |
| T3 | Triiodothyronine |
| T4 | Thyroxine |
| TSPO | Translocator Protein |
| TPO | Thyroid Peroxidase |
| TSH | Thyroid Stimulating Hormone |
| TSPO | Translocator Protein |
| USB | Universal Serial Bus |
| USP | US Pharmacopoeia |
| VC | Vital Capacity |
| WOCBP | Women of Childbearing Potential |

REGIMEN-SPECIFIC APPENDIX (RSA) SUMMARY

Regimen-Specific Appendix [B]

For verdiperstat (also known as BHV-3241).

Rationale and RSA Design

The proposed study is based on cumulative preclinical and clinical studies that implicate myeloperoxidase (MPO) activity in the onset and progression of neurodegenerative diseases and suggest treatment with verdiperstat at a dosage of 600 mg twice daily (BID) has the potential to slow neurodegeneration in Amyotrophic Lateral Sclerosis (ALS).

Allocation to Treatment Regimens

Participants must first be screened under the Master Protocol before they are randomized to an RSA. As soon as pre-defined criteria for futility for the RSA are met, or the target number of randomized participants for the RSA has been reached, enrollment will stop in the RSA.

Number of Planned Participants and Treatment Groups

The number of planned participants for this regimen is approximately 160.

There are 2 treatment groups for this regimen, active and placebo. Participants will be randomized in a 3:1 ratio to active treatment or placebo (i.e., 120 active: 40 placebo).

Planned Number of Sites

Research participants will be enrolled from approximately 60 centers in the US.

Treatment Duration

The maximum duration of the placebo-controlled portion is 24 weeks.

Follow-up Duration

At the conclusion of the 24-week placebo-controlled period of the study, all participants will either schedule a 28-day follow up phone call and end their participation in the regimen or have the option to receive verdiperstat in the open-label extension (OLE) phase of the study.

The OLE portion of the study will continue until verdiperstat is approved and available in the United States, or Biohaven Pharmaceuticals terminates development of verdiperstat for ALS. At the completion of the OLE, a Follow-up Safety Call should be conducted approximately 28 days after the last dose of study drug.

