| ALSFRS-R Higher Resid. Error | 14 | 155 | 0.000 | 0.022 | 0.284 | 1.050 |
| 10% Mortality Rate | 14 | 155 | 0.000 | 0.025 | 0.286 | 1.046 |
| 20% Mortality Rate | 14 | 155 | 0.000 | 0.023 | 0.294 | 1.046 |
| Alternative Common Treatment Effect (30% Slowing; Mort HR = .70) | | | | | | |
| Base | 15 | 160 | 0.000 | 0.776 | 0.002 | 0.694 |
| Slower Accrual | 27 | 160 | 0.000 | 0.771 | 0.005 | 0.695 |
| Faster Accrual | 11 | 160 | 0.000 | 0.762 | 0.002 | 0.694 |
| Less Dropout | 15 | 160 | 0.000 | 0.745 | 0.003 | 0.694 |
| More Dropout | 15 | 160 | 0.000 | 0.722 | 0.003 | 0.694 |
| Reg. Start Same Time | 18 | 160 | 0.000 | 0.782 | 0.002 | 0.691 |

HEALEY ALS Platform Trial
Regimen-Specific Appendix B, Verdiperstat
Version 6.0 , 02-December-2021
CONFIDENTIAL

| Table 10.2.3: Base and Sensitivity Scenarios with Early Futility Stopping. | | | | | | |
|--|-------------------------------|---------------|----------------------------|----------------------------|-----------------------------|-----------------|
| Sensitivity Scenario | Mean Duration (Months) | Mean N | Prob. Early Success | Prob. Total Success | Prob. Early Futility | Mean DRR |
| Reg. Start 3 Months Apart | 11 | 160 | 0.000 | 0.681 | 0.003 | 0.700 |
| ALSFRS-R Slower Progress | 15 | 160 | 0.000 | 0.754 | 0.003 | 0.693 |
| ALSFRS-R Faster Progress | 15 | 160 | 0.000 | 0.791 | 0.002 | 0.694 |
| ALSFRS-R Lower Resid. Error | 15 | 160 | 0.000 | 0.793 | 0.003 | 0.692 |
| ALSFRS-R Higher Resid. Error | 15 | 160 | 0.000 | 0.758 | 0.003 | 0.694 |
| 10% Mortality Rate | 15 | 160 | 0.000 | 0.782 | 0.003 | 0.693 |
| 20% Mortality Rate | 15 | 160 | 0.000 | 0.799 | 0.003 | 0.695 |
| Alternative Treatment Effect No Mort. Benefit (30% Slowing; Mort HR = 1.0) | | | | | | |
| Base (5% Mort. Rate) | 15 | 160 | 0.000 | 0.731 | 0.003 | 0.708 |
| 10% Mort. Rate | 15 | 160 | 0.000 | 0.695 | 0.004 | 0.721 |
| 20% Mort. Rate | 15 | 160 | 0.000 | 0.602 | 0.007 | 0.749 |
| Alternative Treatment Effect Worse Mort. (30% Slowing; Mort HR = 1.3) | | | | | | |
| Base (5% Mort. Rate) | 15 | 160 | 0.000 | 0.683 | 0.004 | 0.722 |
| 10% Mort. Rate | 15 | 160 | 0.000 | 0.592 | 0.008 | 0.750 |
| 20% Mort. Rate | 15 | 160 | 0.000 | 0.411 | 0.015 | 0.803 |

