# 1. Governing Documents

This Regimen-specific Statistical Analysis Plan (R-SAP) for the verdiperstat regimen (RGB) specifies any modification from the default outcome measures, analysis samples, and planned analyses for the placebo-controlled period of the HEALEY ALS Platform Trial as specified in the Master SAP (M-SAP). The M-SAP and this R-SAP supplement the Master Protocol, the "ALS Master Protocol Recommended Statistical Analysis, Design and Simulation Report" (Appendix 1 to the Master Protocol), and the RGB Regimen-specific Appendix (RSA). Please refer to the Master Protocol and the RGB RSA for details on the rationale for the study design, eligibility criteria, conduct of the trial, clinical assessments and schedule of assessments, definitions and reporting of adverse events, data management conventions, and regulatory oversight and compliance procedures. The "ALS Master Protocol Recommended Statistical Analysis, Design and Simulation Report" (MPRDR) and any regimen-specific deviations described in the RGB RSA and this R-SAP are authoritative in defining the primary and interim analyses. In case of discrepancies between the RGB RSA and this R-SAP concerning use of shared placebos, this R-SAP is authoritative. In case of discrepancies between either SAP and the Master Protocol and the RGB RSA concerning matters of analysis other than the primary and interim analyses and use of shared placebos, the M-SAP and this R-SAP are authoritative. In case of discrepancies between the M-SAP and this R-SAP, this R-SAP is authoritative. On all matters not related to analysis, the Master Protocol and the RGB RSA are authoritative. The following table describes relationships among the relevant documents in adjudicating possible discrepancies with higher numbers indicating greater authority.

Issues potentially requiring adjudication	Master Protocol	RGB RSA	MPRDR	M-SAP	RGB R-SAP
Use of shared placebos	1	4	2	3	5
Primary and interim analysis specifications not related to use of shared placebo	1	5	4	2	3
Statistical analysis specifications not related to use of shared placebo or primary and interim analyses	1	3	2	4	5
All matters not related to statistical analysis	4	5	1	2	3

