# 6. Statistical Methodology

#### 6.1 Analysis Sets

The ITT analysis set is henceforth referred to as the Full Analysis Set (FAS) and defined as follows:

• Full Analysis Set (FAS): Participants who were randomized within RGB plus placebo participants from specified regimens, classified according to their randomized treatment assignment. Observations made after premature permanent discontinuation of study drug are included in this sample, should such participants remain on study. Observations completed after regimen data lock are excluded. Participants determined to not meet ALS diagnostic criteria are excluded.

The definition of the STF analysis set is revised as follows:

Safety Full (STF) Set: Participants who initiated treatment within RGB plus placebo
participants from specified regimens who are not known to be ineligible for RGB and who
initiated treatment in their respective regimen, classified according to the treatment they
actually received. Observations made after premature permanent discontinuation of study
drug are included in this sample, should such participants remain on study. Observations
completed after regimen data lock are excluded.

An analysis set restricting shared placebo participants to those regimens in which study drug is administered by the same route as RGB is defined as follows:

• Efficacy Common Mode of Administration (ECM) Set: The subset of participants in the FAS analysis set who are in regimens in which study drug is administered by the same route as RGB.

The definitions of the ECC, ERO, STN, and SRO analysis sets are the same as described in the M-SAP with reference to the ITT analysis set now referencing the FAS analysis set. The following analysis set is specific to RGB:

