Efficacy Per-protocol (EPP) Set: The subset of participants in the FAS analysis set who initiated study treatment and who were not involved in protocol deviations that affected the scientific integrity of the trial as documented prior to data lock, classified according to the treatment they actually received. Inclusion or exclusion from the EPP analysis set of any participant for whom treatment assignment was unblinded prior to data lock will be governed by the prespecified criteria above. If a participant's data is truncated for inclusion in the EPP analysis set due to non-adherence to protocol-specified dosing, clinical events observed up to 28 days after the censoring event will be included in the EPP analysis set. For all other events leading to truncation of a participant's data, no events beyond that date will be included. Data from placebo participants shared from other regimens will not be truncated due to non-adherence to protocol-specified dosing.

•

Applicable analysis sets (FAS, ECM, EPP, STF, and STN) will include shared placebo participants from regimens A and C only. Data from shared placebo participants will include visits and events that occurred on or before the date of the final placebo-controlled period follow-up of a regimen A, B, or C participant. As only concurrently enrolling regimens are

contributing to efficacy analyses, the FAS and ECC analysis sets are synonymous and only the FAS analysis set will be referenced. As regimen A is administered by subcutaneous injection and regimen C is administered orally, only regimen C will contribute shared placebo participants for the ECM and STN analysis sets.

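### If applied to the regimen-only safety set (about 120 v 40), SAP 6.6.1's delta-method interval gives no variance to a placebo arm without events, and so shows apparent harm too often

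*SAP*

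**What the plan says.** SAP 6.6.1 starts from the master plan: its TEAE analyses "are the same as specified in the M-SAP with the following revisions". One revision concerns incidence rates per 100 participant-years. Arms are compared by differences, not ratios, and the estimates "will include comparison-wise 95% confidence intervals with variance estimates obtained by the delta method". They are given for six overall TEAE classes and for "TEAEs with at least 5% prevalence in the active arm". The section says that differences in the proportions affected will not be tested. It sets no minimum placebo count and no rule for an arm with no events. It does not say which safety sets the intervals are for.

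The RSA Summary plans 3:1 randomization, 120 active and 40 placebo. SAP 6.1 states that "Applicable analysis sets (FAS, ECM, EPP, STF, and STN) will include shared placebo participants from regimens A and C only". The regimen-only safety set (SRO) is not in that list, so it would hold about 40 placebo participants. Its definition is deferred: "The definitions of the ECC, ERO, STN, and SRO analysis sets are the same as described in the M-SAP". The M-SAP is not among the documents available for review.

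**The concern.** A first-order delta-method variance for a rate is estimated from that arm's own events. With no events the estimate is zero, and the interval treats the placebo rate as known to be exactly zero. With 40 placebo participants, an empty placebo cell is common for terms of low incidence, even when the drug has no effect. The 5% filter looks only at the active arm, so such terms can still be displayed.

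Readers use labelled 95% intervals to separate drug effects from chance. In a regimen-only table, some would point to harm because of the 3:1 allocation and the variance formula. The error is one-sided: at 5% incidence in both arms the interval almost never lies below zero.

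**Working it through.** **Inputs.** From the RSA Summary: 120 active, 40 placebo and 24 weeks. From SAP 6.6.1: rate differences, 95% level, delta-method variance, and a filter of 5% of 120 = 6. Assumed: full follow-up of 0.46 years each (Ta = 55.2 and Tp = 18.4 participant-years), one event per affected participant, equal true incidence in the arms, and 40 placebo participants each in regimens A and C. The documents give no coverage figure to reproduce.

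**Formula.** With a active and p placebo events, the interval per 100 participant-years is

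100 × [(a/Ta − p/Tp) ± 1.96 × √(a/Ta² + p/Tp²)].

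If p = 0, the ratio of estimate to standard error is (a/Ta) / (√a/Ta) = √a, whatever the exposure. It exceeds 1.96 from a = 4 (√4 = 2.00), but not at a = 3 (1.73).

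**Examples, 120 v 40.**

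| Active v placebo | Delta-method interval | Fisher exact p |
|---|---|---|
| 3 v 0 | 5.4 (−0.7 to 11.6) | 0.57 |
| 4 v 0 | 7.2 (0.15 to 14.4) | 0.57 |
| 6 v 0 | 10.9 (2.2 to 19.6) | 0.34 |
| 12 v 1 | 16.3 (0.03 to 32.6) | 0.19 |

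With equal rates, six events all fall in the active arm with probability 0.75⁶ = 17.8%. The last row shows that the problem is not confined to exact zeros.

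Other intervals for 6 v 0 include zero:

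- The score interval is −10.0 to 23.7.
- MOVER with Jeffreys Poisson limits takes limits from gamma quantiles with shape count + 0.5. The active lower limit is 2.504/55.2 = 4.54 per 100 and the placebo upper limit is 2.512/18.4 = 13.65 per 100. The lower bound is 10.87 − √[(10.87 − 4.54)² + 13.65²] = −4.2.

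**Frequency with no true difference, 120 v 40.** Exact binomial enumeration over all pairs of counts:

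| Incidence in both arms | Wholly above zero, no filter | Meets filter and lies above zero |
|---|---|---|
| 3% | 14.4% | 4.5% |
| 5% | 11.5% | 7.6% |
| 10% | 5.8% | 5.8% |

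The nominal figure for the first column is 2.5%. At 5%, the zero cell alone gives 0.558 (6 or more of 120) × 0.95⁴⁰ = 0.558 × 0.129 = 7.2%. Low non-zero placebo counts supply the rest of the 7.6%. At 5% with no filter, the interval lies below zero 0.3% of the time.

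**Sets with shared placebo, no filter.** With 80 placebo participants (STN, assumed) the interval lies above zero 4.9% of the time at 3% and 3.8% at 5%. With 120 (STF, assumed) it is about 2%. At 120 v 120 with equal exposure, the delta and score statistics for no difference are both (a − p)/√(a + p), so the two methods agree on whether zero is excluded.

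**Alternatives at 120 v 40, 5% in both arms, no filter.** The score interval lies above zero 0.2% of the time and below it 3.5%. For MOVER with Jeffreys limits the figures are 1.9% and 2.5%.

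**The case against.** The strongest objection is that the setting is not confirmed. SAP 6.6.1 names no set. The reference in SAP 6.6.2 to all safety samples concerns thyroid results, and the mention of SRO in SAP 6.5.4 concerns time-to-event analyses. The rate model is in the M-SAP. A log-rate model could give no interval at all for an empty cell. If repeat events are counted with a between-participant variance, one participant with many recurrences can bring zero back in: active counts of 1, 1, 1, 1, 1 and 5 against none give a ratio of 1.85. This stands, and it makes the point conditional.

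The M-SAP may also hold a zero-event rule. SAP section 1 says "In case of discrepancies between the M-SAP and this R-SAP, this R-SAP is authoritative", but such a rule could supplement the delta-method sentence without contradicting it, so precedence does not settle the matter. A rule for empty cells alone would still leave cases such as 12 v 1.

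A reader might infer that 29.6% of null terms at 3% incidence are falsely flagged. That figure is conditional on a term meeting the filter, which happens 15.3% of the time; the joint probability is 0.153 × 0.296 = 4.5%. A reader might also blame the interval for the excess among displayed terms with 120 placebo participants (8.4% at 3%, 3.4% at 5%). The score interval gives the same figures there, so that excess comes from selecting rows on the active arm.

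Finally, it is defensible for descriptive safety intervals to lean toward harm. But an interval labelled 95% should behave roughly as one.

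**Conclusion.** The concern holds in a limited form. If the intervals are produced for SRO at about 120 v 40, with a Poisson variance or one event per affected participant, every TEAE that meets the filter with no placebo case gets an interval above zero. With equal incidence and no filter, the upper-side error is roughly two to six times nominal (5.8% to 14.4% against 2.5%) for incidences of 3% to 10%. It is modest with about 80 placebo participants and not present with about 120.

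The documents do not support a wider claim that all the safety tables are affected, or that particular events will be. Syncope is one tempting example, but a term below 6 of 120 gets no row of its own, and RSA 5.9.1.3 reports no syncope in participants given the extended-release formulations. Fatal TEAEs are another, but the 5% mortality in RSA 10.2 is a simulation input that is not tied to fatal TEAEs. The intervals are descriptive and the primary analysis is untouched. The change is still worth making before the tables are produced.

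**What to change.** In SAP 6.6.1, replace the delta-method interval, at least for SRO, with one that is valid at zero and low counts: a score (Miettinen-Nurminen type) interval for the rate difference, or a MOVER interval built from Jeffreys Poisson limits. The second has error rates closer to nominal at 120 v 40. State which safety sets receive the intervals. Keep the 5% filter, so that no row is lost, and footnote that rows are selected on the active arm.

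This needs a small change to the SAP text and the program, and no new data. The price is wider SRO intervals and less sensitivity to real harm. At a true incidence of 10% active v 3% placebo, zero is excluded 51% of the time with the delta method, 31% with MOVER-Jeffreys and 18% with the score interval. Part of the 51% comes from empty placebo cells.
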